3.5 Analysis sets

3.5.1 Enrolled Set

The Enrolled Set (ES) will consist of all subjects who have given informed consent (ie, all subjects screened). The ES will therefore include Screening failures.

3.5.2 Randomized Set

The Randomized Set (RS) will consist of all subjects randomized into the study.

3.5.3 Safety Set

The Safety Set (SS) will consist of all subjects who received at least 1 dose (full or partial) of IMP. The safety analysis will be conducted on the SS.

3.5.4 Full Analysis Set

The Full Analysis Set (FAS) is a subset of the RS and will consist of all subjects who received at least 1 dose (full or partial) of IMP and had a valid Baseline measurement and a post-Baseline measurement for at least 1 efficacy variable (as defined in [Section 2.2.1](#)). The FAS will be used for the supportive and sensitivity analyses of the primary efficacy variable and for all exploratory efficacy analyses.

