15.1 Definition of analysis sets

The Enrolled Set (ES) will consist of all subjects who have given informed consent.

The Randomized Set (RS) will consist of all randomized subjects.

The Safety Set (SS) will consist of all subjects who receive at least 1 dose of the IMP.

The Full Analysis Set (FAS) will consist of all randomized subjects who receive at least 1 dose of the IMP and have a valid measurement of the primary efficacy variable at Baseline and at least one post baseline efficacy assessment.

The Per-Protocol Set (PPS) will consist of all subjects in the FAS who have no important protocol deviation affecting the primary efficacy variable. The subjects with important protocol deviations will be predefined and evaluated during a data evaluation meeting prior to unblinding of the data.

The Pharmacokinetics Per-Protocol Set (PK-PPS) will consist of all randomized subjects who received at least 1 dose of the IMP and have at least 1 quantifiable post-dose plasma concentration.

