15.10 Handling of dropouts or missing data

For the analysis of the primary efficacy variable, non-responder imputation will be used to impute missing data for subjects who have missing data at a specific visit and for subjects who discontinue early from the study during the Treatment Period for any reason. These subjects will be defined as non-responders at all subsequent visits after the time of study discontinuation. In additional sensitivity analyses, subjects who receive specific rescue therapy may also be considered a non-responder from the time that the rescue therapy was taken to the end of the Treatment Period.

Further details on all methods to be used for missing data imputation in the analysis of the efficacy variables will be included in the SAP.

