3.5.5 Per-Protocol Set

The Per-Protocol Set (PPS) is a subset of the FAS, consisting of those subjects who had no IPDs affecting the primary efficacy variable, as confirmed during a pre-analysis review prior to unblinding of the data (at each of the interim and final analyses). All primary efficacy analyses will be performed for the PPS. The PPS will also be used for the supportive and sensitivity analyses of the primary efficacy variable.

Protocol deviations will be reviewed at the DEMs and any exclusions from analysis sets will be documented as described in [Section 3.4](#). It is anticipated that the PPS for the final analysis will differ from the PPS defined at the formal interim analysis as the primary efficacy variable is assessed at Week 12, whereas the formal interim analysis will be based on only 45 of the 80 randomized subjects completing Week 4 of the study. Therefore, all relevant data will not be available at the time of the interim analysis DEM.

The PPS as agreed for the informal interim analysis may similarly be different from the PPS as agreed for the final analysis due to additional information obtained on subjects during the SFU Period.

Following the final DEM, the inclusion into each of the analysis sets for all subjects will be confirmed. The DEM minutes will document the final agreed PPS to be applied to the final analysis, as well as document any changes to the PPS relative to the previously agreed PPS at the interim(s), if applicable.

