4.2 Handling of dropouts or missing data

4.2.1 Efficacy data

There will be no imputation of missing data for the individual components of the HiSCR (abscess count, inflammatory nodule count and draining tunnel (fistula/sinus tract) count).

For subjects with a missing HiSCR due to missing component data at a specific visit, or due to early discontinuation from the study during the Treatment Period, non-responder imputation

(NRI) will be used for the primary analysis of the primary efficacy variable. These subjects will be defined as non-responders at a specific visit or at all subsequent visits after the time of study discontinuation. In additional sensitivity analyses, an ‘observed cases’ analysis will also be performed (no imputation of missing HiSCR) and subjects who receive specific rescue therapy will also be considered a non-responder from the time that the rescue therapy was taken to the end of the Treatment Period ([Section 8.2.3](#)).

For the hsCRP data, measurements that are below the limit of quantification (BLQ) will be imputed with half of the lower limit of quantification (LLOQ) for the purpose of calculating summary statistics, changes from Baseline and ratio to Baseline.

The handling of any missing data for the other exploratory efficacy data is described or referenced in the respective sections where the analysis of this data is described.

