8.2.3 Supportive and sensitivity analyses of the primary efficacy variable

The primary efficacy analysis set is the PPS, however the primary analysis and all supportive and sensitivity analyses of the primary efficacy variable will be repeated using the FAS.

The comparison of the BKZ treatment group to the ADA treatment group is described specifically in this section as a sensitivity analysis, however, it must be noted that the results from the BKZ versus ADA comparison will be presented for completeness in each of the sensitivity analyses described in [Section 8.2.3.1](#) to [8.2.3.10](#) below.

Further analyses of the primary efficacy variable may be performed adjusting for other Baseline covariates. Results from any additional analyses will not be used as a substitute for the planned analyses, but may be used as supplemental information for the CSR. Should such analysis become necessary they will be defined in a further amendment to this SAP.

All sensitivity analyses of the primary efficacy variable are specified in the sections below.

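### Dosed subjects never assessed after Baseline fall out of the FAS and the PPS, although the NRI rule would count them as Week 12 non-responders; the group is probably very small

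*SAP*

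**What the plan says.** **Who is in the sets.** SAP 3.5.4 admits to the FAS those randomised, dosed subjects who "had a valid Baseline measurement and a post-Baseline measurement for at least 1 efficacy variable". Protocol 15.1 asks that they "have a valid measurement of the primary efficacy variable at Baseline and at least one post baseline efficacy assessment". SAP 3.5.5 adds: "The Per-Protocol Set (PPS) is a subset of the FAS". The primary analysis uses the PPS (protocol 15.5, SAP 8.2.2), and SAP 8.2.3 says that "the primary analysis and all supportive and sensitivity analyses of the primary efficacy variable will be repeated using the FAS".

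**What happens to missing outcomes.** In SAP 4.2.1 the trigger for NRI in the primary analysis reads "For subjects with a missing HiSCR due to missing component data at a specific visit, or due to early discontinuation from the study", and the consequence is: "These subjects will be defined as non-responders at a specific visit or at all subsequent visits after the time of study discontinuation". Protocol 15.10 agrees: "non-responder imputation will be used to impute missing data for subjects who have missing data at a specific visit", with early discontinuation for any reason treated the same way. The frequentist NRI model in SAP 8.2.3.7 also imputes non-response after withdrawal.

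**What was already changed.** SAP 3.9 records that the FAS condition was widened to any efficacy variable, so that one missing HiSCR component would not exclude a subject.

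**The concern.** Under NRI, a subject who takes a dose and is never seen again has a known analysis value at Week 12: no response. The set definition removes that subject before the rule can apply. The most extreme early failures are then absent from the denominator instead of counted in it.

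Two things are at stake. First, inclusion depends on a post-randomisation event that treatment can influence, for example through early intolerance. Leaving out non-responders can only raise an arm's response rate, so unequal loss shifts the comparison. Second, the FAS is the planned check on a per-protocol primary analysis, and here it shares the exclusion it might be expected to expose. No planned efficacy analysis uses the Randomized Set or all dosed subjects.

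**Working it through.** **Inputs.** From SAP 2.4: 40 bimekizumab and 20 placebo subjects; assumed rates of 70% and 27.6%; placebo prior Beta(5.52, 14.48); vague bimekizumab prior; success if the posterior probability of a higher bimekizumab rate is at least 97.5%; stated probability of success at least 99%. Neither document says how many dosed subjects will have no post-Baseline measurement, so the shares below are assumptions.

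**Method.** With y responders of n on bimekizumab and x of m on placebo, the posteriors are Beta(y + 0.01, n − y + 0.01) and Beta(5.52 + x, 14.48 + m − x). The 0.01 stands in for the near-flat logit prior, and the Hurley Stage term is omitted. Probability of success sums the binomial probabilities of all (y, x) that reach 97.5%.

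**Step 1: the plan's own figure.** With n = 40 at 70% and m = 20 at 27.6%, the result is 98.7%, which agrees with the SAP's 99% to the nearest point.

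**Step 2: response rates.** Hold bimekizumab responders at 0.70 × 40 = 28.

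| Non-responders left out | Rate | Change (points) |
|---|---|---|
| 0 | 28/40 = 70.0% | 0 |
| 1 | 28/39 = 71.8% | +1.8 |
| 2 | 28/38 = 73.7% | +3.7 |

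Placebo expects 0.276 × 20 = 5.52 responders. Leaving out one non-responder gives 5.52/19 = 29.1%. If two bimekizumab subjects and one placebo subject are left out (5% of each arm), the difference goes from 70.0 − 27.6 = 42.4 to 73.7 − 29.1 = 44.6 points, a rise of 2.2. If only the two bimekizumab subjects are lost, the rise is 3.7. If only the placebo subject is lost, the difference falls by 29.1 − 27.6 = 1.5 points, so the direction is not fixed.

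**Step 3: probability of success.** Let a share e of each arm never be assessed, and let 70% and 27.6% apply to the rest. Counting everyone gives an expected difference of 42.4 × (1 − e).

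| e (assumed) | Difference, counted | Success, left out | Success, counted |
|---|---|---|---|
| 2.5% | 41.3 | 98.9% | 98.2% |
| 5% | 40.3 | 98.7% | 97.4% |
| 10% | 38.2 | 98.8% | 95.3% |

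The left-out column uses 39/20, 38/19 and 36/18 subjects.

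**Step 4: near the threshold.** Here subjects are lost on bimekizumab only.

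- Placebo 7/20: 21/40 gives 0.9746 (fail) and 21/39 gives 0.9804 (pass).
- Placebo 5/20: 18/40 gives 0.9623 (fail) and 18/38 gives 0.9753 (pass).
- Placebo 6/20: 20 responders are needed whether n is 40, 39 or 38, so losing one or two subjects changes nothing.

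**Step 5: no treatment effect.** With both true rates at 27.6% and nobody lost, success has probability 1.2%. With 5% or 10% lost on bimekizumab only, it is 1.4% or 1.1% when they are left out, and 0.8% or 0.5% when they are counted.

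**The case against.** - **Leaving early is not the exclusion criterion.** A reader might infer that everyone who stops before the first efficacy visit at Week 2 is lost. The documents do not support that. One post-Baseline measurement of any efficacy variable qualifies, with no time limit. Early leavers are asked back for the Week 12 Visit and the safety follow-up assessments (protocol 8.11, SAP 4.4), and both include lesion counts and questionnaires. An unscheduled visit may also include a lesion count (protocol 8.12). Only subjects never assessed again are affected. This stands, and it makes 5% per arm an upper-end assumption for a group that may be 0 or 1 subject.
- **The two rules do not formally contradict each other.** NRI assigns outcomes within a set; it does not say who belongs. This stands as logic. The point is that the set withholds subjects whose outcome the plan can already assign.
- **The primary result may not change.** SAP 3.4 lists missing data, visit schedule and withdrawal criteria among the important deviation classes, so the data evaluation meeting could still remove such a subject from the PPS. This stands, and the remedy must cover it.
- **The gap would be visible.** SAP 5.1 reports the size of each set by arm against the Randomized Set. This is true, but it shows a count and gives no analysis with those subjects included.
- **The borderline cases were selected.** They lie far from the planned 70% against 27.6%. This stands.

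**Conclusion.** The point holds as a gap in the set definition, with a small likely effect. The post-Baseline condition takes out of the FAS, and so out of the PPS, subjects whom NRI would classify without further data, and nothing elsewhere in either document puts them back. SAP 3.9 narrowed the gap without closing it.

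One or two subjects move the bimekizumab rate by 1.8 or 3.7 points. At the planned rates, counting such subjects lowers the probability of success by 98.9 − 98.2 = 0.7 points (2.5% never assessed) to 98.8 − 95.3 = 3.5 points (10%). The conclusion could change only near the 97.5% threshold. A reader might infer that the plan is materially biased toward bimekizumab. The documents do not support this: they give no rate, loss on placebo works the other way, and the chance of a false success stays below 2.5% in the cases examined.

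These figures rest on assumed shares, on planned arm sizes rather than a reduced PPS, and on a model without the Hurley Stage term.

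**What to change.** 1. For the NRI-based HiSCR analyses, use all randomised subjects who received at least one dose and have a Baseline lesion count, and apply NRI to any missing Week 12 HiSCR. The Baseline condition is met before dosing, so treatment cannot affect it.
2. State that having no post-Baseline data because of discontinuation is not in itself a deviation that removes a subject from the PPS for the NRI analysis. Without this, the change may reach only the supportive analysis.
3. Report by arm the number of dosed subjects never assessed after Baseline. If it is zero, the results are unaffected.
4. Keep the existing FAS for observed-case and exploratory analyses. It is also the denominator for the skin pain response (SAP 8.3.3) and the parent of the PD-PPS (SAP 3.5.7).

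**Cost.** No new data or visits are needed. Response rates become slightly less favourable if such subjects exist, and HiSCR needs a second set definition. The current SAP amendment draws on the second unblinded interim analysis (SAP 3.9, 4.5.2), so a change to an efficacy set now should be documented as made after that look, or added as a supportive analysis beside the existing sets.

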3.5.5 Per-Protocol Set

The Per-Protocol Set (PPS) is a subset of the FAS, consisting of those subjects who had no IPDs affecting the primary efficacy variable, as confirmed during a pre-analysis review prior to unblinding of the data (at each of the interim and final analyses). All primary efficacy analyses will be performed for the PPS. The PPS will also be used for the supportive and sensitivity analyses of the primary efficacy variable.

Protocol deviations will be reviewed at the DEMs and any exclusions from analysis sets will be documented as described in [Section 3.4](#). It is anticipated that the PPS for the final analysis will differ from the PPS defined at the formal interim analysis as the primary efficacy variable is assessed at Week 12, whereas the formal interim analysis will be based on only 45 of the 80 randomized subjects completing Week 4 of the study. Therefore, all relevant data will not be available at the time of the interim analysis DEM.

The PPS as agreed for the informal interim analysis may similarly be different from the PPS as agreed for the final analysis due to additional information obtained on subjects during the SFU Period.

Following the final DEM, the inclusion into each of the analysis sets for all subjects will be confirmed. The DEM minutes will document the final agreed PPS to be applied to the final analysis, as well as document any changes to the PPS relative to the previously agreed PPS at the interim(s), if applicable.

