15.5 Planned efficacy analyses

The primary efficacy analyses will be based on the PPS.

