3.4 Protocol deviations

Important protocol deviations (IPDs) are deviations from the protocol which potentially could have a meaningful impact on the primary objective of the study. The criteria for identifying such protocol deviations will be defined within the IPD document which is part of the data cleaning plan. Important protocol deviations will be classified as follows:

- Inclusion/exclusion criteria deviations
- Administration of prohibited concomitant medications
- Deviations relating to withdrawal criteria
- Visit schedule deviations

- Study drug administration deviations (including incorrect treatment received, handling and storage deviations and incorrect dosage received)
- Treatment non-compliance
- Procedural non-compliance
- Missing data
- Other

Important protocol deviations will be reviewed as part of the ongoing data cleaning process and data evaluation.

At least 3 data evaluation meetings (DEMs) will be performed for this study at the following time points:

- Prior to the informal unblinded interim analysis planned after approximately 45 subjects have completed 4 weeks of the study.
- Prior to the informal unblinded interim analysis planned after the last subject (excluding 2 subjects from site 101 in Australia who entered the study outside of the original planned recruitment period) has completed 12 weeks of the study or has discontinued early.
- Prior to the final analysis after all subjects have completed the SFU period and data have been verified/coded/entered into the database

Additional DEMs may be conducted as deemed necessary.

The purpose of these DEM reviews will be to review all protocol deviations, define the analysis sets, and check the quality of the data. The reviews will also help decide how to manage problems in the subjects' data (eg, missing values and withdrawals).

Accepted deviations from theoretical time points will be described in the appropriate documents and included in the Study Master File. After the pre-analysis review, resolution of all issues, and documentation of all decisions (including inclusion into each of the analysis sets) at the final DEM, the database will be locked.

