- Subjects randomized to bimekizumab who received any doses of adalimumab during the Treatment Period, but at least 1 dose of bimekizumab, will be assessed at the DEM for the treatment group assignment, as it will depend on how many doses of each of the treatments were taken and at what time point during the study

- Subjects randomized to placebo who received at least 1 dose of adalimumab will be summarized in the ‘ADA’ treatment group
- Subjects randomized to adalimumab who received placebo throughout the Treatment Period will be summarized in the ‘PBO’ treatment group
- Subjects randomized to adalimumab who received any doses of placebo during the Treatment Period, but at least 1 dose of adalimumab, will be summarized in the ‘ADA’ treatment group
- Subjects randomized to adalimumab who received any doses of bimekizumab during the Treatment Period, but at least 1 dose of adalimumab, will be assessed at the DEM for the treatment group assignment, as it will depend on how many doses of each of the treatments were taken and at what time point during the study
- Subjects randomized to placebo who received at least 1 dose of adalimumab and at least 1 dose bimekizumab will be assessed at the DEM for the treatment group assignment, as it will depend on how many doses of each of the active treatments were taken and at what time point during the study

Subjects receiving the incorrect treatment at a particular visit will be excluded from the PPS, PD-PPS and the PK-PPS as this would be considered as an IPD. Subjects may be excluded from the analysis at a particular visit (or visits) only or overall, following discussion at the DEMs, and will be included in the analyses according to their randomized treatment (which would be equivalent to an analysis according to their actual treatment)

All statistical analyses of the PK and immunological data will be conducted according to the actual treatment received, ie, treatment assignment for the PK-PPS will be based on actual treatment.

Similarly, all statistical analyses of the PD data will be conducted according to the actual treatment received, ie, treatment assignment for the PD-PPS will be based on actual treatment.

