8.2.2 Primary analysis of the primary efficacy variable

The primary efficacy analysis of the primary efficacy variable will be based on the PPS.

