8.2.2.1 Bayesian modeling

The primary Bayesian model (a logistic regression model for the mean binary response $E[y]$) will be:

$$\ln\left(\frac{E(y)}{1-E(y)}\right) = \beta_{PBO} X_{PBO} + \beta_{BKZ} X_{BKZ} + \beta_{ADA} X_{ADA} + \beta_{hII} X_{hII} + \beta_{hIII} X_{hIII} \quad (1)$$

where X_{PBO} , X_{BKZ} and X_{ADA} are dummy variables taking the value 1 or 0 according to whether or not each subject is in the PBO, BKZ or ADA treatment groups respectively, X_{hII} and X_{hIII} are dummy variables taking the value 1 or 0 according to whether or not each subject is in the Baseline Hurley Stage II or III groups respectively. Proof-of-concept (PoC) will be declared in this study if the estimated posterior probability, using the above model, of the difference in response rates between the BKZ and PBO treatment groups is 0.975 or greater.

For parameter estimation, the following constraint will be used:

$$\beta_{hII} = -\beta_{hIII}$$

giving the model:

$$\ln\left(\frac{E(y)}{1-E(y)}\right) = \beta_{PBO} X_{PBO} + \beta_{BKZ} X_{BKZ} + \beta_{ADA} X_{ADA} + \beta_{hII} (X_{hII} - X_{hIII}) \quad (2)$$

so that the influence of Baseline Hurley Stage on the model estimated treatment group mean responses are more evident. To see this, note that if $\bar{\eta}_{PBO}$ represents the mean of the logit responses from model (2) for the PBO subjects (the simple “arithmetic” mean) then $\text{logit}^{-1}(\bar{\eta}_{PBO})$ is the response probability associated with that mean logit response and is 1 type of estimate of the PBO group response rate. Accordingly:

- $p_{PBO} | p_{hII}^{PBO}, p_{hIII}^{PBO} = \text{logit}^{-1}(\bar{\eta}_{PBO}) = \text{logit}^{-1}(\beta_{PBO} + \beta_{hII}(p_{hII}^{PBO} - p_{hIII}^{PBO}))$ represents the probability of response in the PBO group conditional on p_{hII}^{PBO} and p_{hIII}^{PBO} , which are the Baseline Hurley Stage subject proportions chosen to evaluate the estimated PBO group mean at (here the observed proportions are chosen)
- $p_{BKZ} | p_{hII}^{BKZ}, p_{hIII}^{BKZ} = \text{logit}^{-1}(\bar{\eta}_{BKZ}) = \text{logit}^{-1}(\beta_{BKZ} + \beta_{hII}(p_{hII}^{BKZ} - p_{hIII}^{BKZ}))$ represents the probability of response in the BKZ group conditional on p_{hII}^{BKZ} and p_{hIII}^{BKZ} which are the Baseline Hurley Stage subject proportions chosen to evaluate the estimated BKZ group mean at (here again the observed proportions are chosen)

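### The only formal success decision is taken on the Per-Protocol Set, which can drop subjects for post-randomisation deviations, and the Full Analysis Set repeat plays no part in it

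*SAP*

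**What the plan says.** Both documents put the primary analysis on the Per-Protocol Set (PPS). Protocol 15.5: "The primary efficacy analyses will be based on the PPS". SAP 3.5.5: "All primary efficacy analyses will be performed for the PPS". SAP 8.2.2: "The primary efficacy analysis of the primary efficacy variable will be based on the PPS". The success rule is tied to that model in SAP 8.2.2.1: "Proof-of-concept (PoC) will be declared in this study if the estimated posterior probability, using the above model" for bimekizumab against placebo reaches 0.975. SAP 3.1 limits formal testing to this variable.

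The PPS is the Full Analysis Set (FAS) minus subjects with an important protocol deviation (IPD) that affects the primary variable (SAP 3.5.5). On what counts as an IPD, SAP 3.4 says: "The criteria for identifying such protocol deviations will be defined within the IPD document which is part of the data cleaning plan". The classes it lists include prohibited medication, dosing errors, non-compliance and missing data. For wrong treatment, SAP 3.6 adds: "Subjects may be excluded from the analysis at a particular visit (or visits) only or overall, following discussion at the DEMs".

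For missing outcomes, Protocol 15.10 says: "For the analysis of the primary efficacy variable, non-responder imputation will be used to impute missing data". SAP 4.2.1 applies the same non-responder imputation (NRI) in the primary analysis.

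The primary analysis and all its sensitivity analyses are repeated on the FAS to show the effect of IPDs (SAP 8.2.3 and 8.2.3.1). Neither document says what follows if the two sets disagree. The FAS itself needs at least one post-Baseline efficacy measurement (SAP 3.5.4).

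**The concern.** Randomisation protects a comparison of the groups as randomised. A set defined partly by what happens after randomisation can lose that protection if deviations depend on treatment or on response. Here the trial's only formal conclusion rests on such a set.

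A subject excluded for an IPD is removed whatever the outcome. An observed Week 12 HiSCR is discarded, and a missing one that NRI would count as a failure is discarded too. Missing data is itself an IPD class, so the exclusion rule and the NRI rule can claim the same subject, and the SAP does not say which prevails. A treated subject with no post-Baseline efficacy measurement is outside the FAS as well, so NRI does not reach that subject in either set.

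At stake is whether proof of concept is declared on a selected subset while the less selected analysis has no say.

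**Working it through.** **Inputs.** 40 bimekizumab and 20 placebo subjects; true rates of 70% and 27.6%; placebo prior Beta(5.52, 14.48); bimekizumab prior N(0, 10000) on the logit scale; threshold 0.975 (SAP 2.4 and 8.2.2.1). The documents give no IPD rate, so the number and type of exclusions below are assumptions. The Hurley term is omitted.

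**Method.** With x_P of n_P placebo responders, the placebo posterior is Beta(5.52 + x_P, 14.48 + n_P − x_P). The bimekizumab posterior is its binomial likelihood times the vague logit prior. Success means P(p_B > p_P) ≥ 0.975. The probability of success sums over all outcomes, weighted by Binomial(40, true rate) × Binomial(20, 0.276).

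**The plan's own figure.** With no exclusions this gives 98.7% at the planned rates. SAP 2.4 states at least 99%, so the simplified model is close enough to use.

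**One data set.** With 5/20 placebo responders:
- 18/40 on bimekizumab: 0.962, fail.
- Two bimekizumab non-responders excluded (18/38): 0.975 (0.9753), success.
- One placebo non-responder excluded as well (18/38 against 5/19): 0.970, fail.
- 19/40 with nobody excluded: 0.977, success.

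**Probability of success (%)**, by true bimekizumab rate against placebo 27.6%:

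| Exclusion pattern | 70% | 50% | 27.6% |
|---|---|---|---|
| None (40/20) | 98.7 | 57.5 | 1.2 |
| 10% per arm, unrelated to outcome (36/18) | 98.8 | 56.2 | 1.2 |
| 2 bimekizumab non-responders | 99.4 | 64.6 | 2.2 |
| 2 bimekizumab and 1 placebo non-responder | 99.3 | 60.7 | 1.4 |
| 4 bimekizumab and 2 placebo non-responders | 99.7 | 70.3 | 2.3 |
| 2 placebo non-responders | 98.2 | 50.0 | 0.7 |
| 2 bimekizumab responders | 97.6 | 45.3 | 0.5 |

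At a true 50% the shifts run from 45.3 − 57.5 = −12.2 points to 70.3 − 57.5 = +12.8 points. At the planned rate they run from −1.1 to +1.0.

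**Requiring both sets.** The three patterns that remove bimekizumab non-responders return to 98.7 / 57.5 / 1.2%. With two bimekizumab responders excluded, the result is 97.6 / 45.3 / 0.5%.

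**The case against.** The PPS was prespecified, and protocol and SAP agree on it. Protocol 15.1 provides a safeguard: "The subjects with important protocol deviations will be predefined and evaluated during a data evaluation meeting prior to unblinding of the data". SAP 3.5.5 confirms membership before unblinding at each analysis and has changes minuted. The full FAS repeat is planned. Exclusion unrelated to outcome has almost no effect, and the 18/38 example is on a knife edge. All of this stands, and it limits the point. Blinded review prevents deliberate selection, but it does not remove bias when deviations themselves depend on treatment or response.

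A reader might infer more than the documents support:
- *That excluded subjects in general escape NRI.* NRI concerns only a missing HiSCR or early discontinuation. A subject given the wrong treatment may have an observed Week 12 result, which the FAS would simply use. Dropouts without a relevant IPD stay in the PPS as non-responders.
- *That the PPS inflates false success.* A figure of 6.9% can be produced, but it needs 20% of bimekizumab subjects excluded, all of them non-responders, and nobody excluded on placebo. No document suggests this pattern.
- *That interim results shaped the PPS.* Protocol 7.9 and 15.11 separate the unblinded team and bar disclosure to the blinded team. What remains is narrower. The final PPS may differ from the one agreed for the second interim, and nothing says explicitly that those who settle it have no access to that interim's results.

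It can also be objected that changing the decision set after an unblinded interim is itself a post hoc change. That is fair, and it is why the fix requires disclosure and agreement of both sets. Rescue is a separate matter: a rescued subject's observed response counts in the primary analysis under either set, unless the subject is excluded for an IPD.

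**Conclusion.** The point holds and is worth fixing. The sole success decision rests on a set that post-randomisation events can shape, and the FAS result has no stated role in it. Size and direction cannot be determined, because the IPD criteria sit in a separate document and no rate is given. Under the assumed patterns, the effect is negligible if exclusions are unrelated to outcome. It is about one point either way at the planned effect, and up to about 12 or 13 points either way at a true rate of 50%. With no true difference, every pattern in the table stays below 2.5%. The documents do not show that the PPS favours bimekizumab, or that the trial's conclusion would be wrong.

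**What to change.** In Protocol 15.1 and 15.5 and SAP 3.5.4, 3.5.5, 8.2.2 and 8.2.3.1, apply the 97.5% rule to all randomised subjects who received IMP and have a Baseline lesion count, analysed as randomised, with NRI for missing HiSCR. Make the PPS the sensitivity analysis. This also settles, for the decision, the overlap between missing data as an IPD class and NRI.

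SAP 3.9 and 15.1.1 indicate that the second interim has already taken place. If it has been unblinded, record the change in SAP 3.9 as made after that interim, report both sets, and claim success without qualification only if both reach 97.5%. Add to SAP 3.5.5 that those who settle the final PPS have no access to interim results.

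The cost is a SAP amendment and, if the change counts as significant under Protocol 16.5, a protocol amendment with its approvals. Programming is minor, since every analysis of the primary variable is already planned on the FAS; the new set adds only treated subjects with no post-Baseline efficacy measurement. The estimate may be less favourable. The both-sets rule lowers the chance of an unqualified claim in some patterns, for example from 98.7% to 97.6% at the planned effect if two bimekizumab responders are excluded from the PPS.
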